6. SUBJECT RECRUITMENT & SCREENING

Based on a power analysis, 64 participants are needed with an expected attrition rate of 20% increasing the total number of participants to 78, with 26 in each of three groups.

Participants will be fluent in English, males and females age 18 years and older. The study will include participants from any race or ethnicity that meet eligibility criteria and demonstrate a positive Phalen's Test or positive Tinel's Test. The study population includes individuals who have symptoms of or have received a diagnosis of carpal tunnel syndrome, or experience forearm wrist hand pain and currently not receiving treatment. If participant has symptoms in both extremities, the researcher will use each extremity as a separate unit and apply corresponding intervention to both extremities.

Participants will be recruited using snowballing and judgmental sampling via word-of-mouth, flyers, emails, and social media with a \$5.00 gift card provided per visit for each of the five visits for the study. Flyers will be distributed throughout the Southern California area due to proximity but participants may come from any region if satisfying inclusion criteria and time commitment. Flyers will be placed in, but not limited to, common public places such as pet grooming places, community postings, manufacturing facilities, clinics, hair stylists, dental hygienists, sonographers, office buildings, and more. The principal investigator or appropriate personnel for Loma Linda University, and by the student researcher or appropriate personnel for the Stanbridge University access will acquire email addresses of potential participants. Specific social media outlets will include posting on but not limited to, Facebook, Instagram, and Twitter, with a website that will be accessed at: carpaltunnelstudy.wordpress.com for information. The contact information of the principal

investigator and student researcher will be available on the flyer with an invitation to contact researchers with any questions about the study.

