8. Randomly assign participants using a random number generator, to one of three groups:
Intervention group, control group, or usual protocol group. A script will be used to control for bias and ensure consistency between groups.

Intervention group:

The student researcher and/or student research assistants who have been trained in Kinesio Tape and application procedures will apply the baseline dorsal application of Kinesio Tape according to determined protocol. The Kinesio Tape will be measured along the participant's lateral epicondyle to metacarpophalanges, the Kinesio Tape then bifurcated. Anchor Kinesio Tape on the dorsal side at the musculotendinous juncture to digits 1 and 5, just past the carpalmetacarpophalangeal joint of digit 1 and metacarpophalange of joint 5, wrist in flexion to stretch the skin, paper off tension (10%). Kinesio Tape application to digits 1 and 5 with carpalmetacarpophalangeal and metacarpophalange flexion during application. Two space correction pieces

applied to both the extensor and flexor surface at 75% stretch, then radially deviate, smooth edges, ulnarly deviate, smooth edges, repeat.

A handout with Kinesio Tape Removal Instructions will be provided (Appendix I). A symptom journal will be provided with instructions to complete daily (Appendix J). A script will be used with participants (Appendix K).

Control group:

The student researcher and/or student research assistants will apply the Sham application of Kinesio Tape, a four-inch strip of Kinesio Tape to the participants' shoulder (scapular spine). A handout with Kinesio Tape Removal Instructions will be provided (Appendix I). A symptom journal will be provided with instructions to complete daily (Appendix J). A script will be used with participants (Appendix K).

Usual protocol group:

The student researcher and/or student research assistants will provide a general wrist cock up splint with instructions to wear nightly and record compliance in a Splint and Exercise journal (Appendix L). Wrist Lumbrical exercises will be demonstrated by the student researcher or student research assistants and a handout with instructions provided (Appendix M). A symptom journal will be provided with instructions to complete daily (Appendix J). A script will be used with participants (Appendix K).

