11. DATA ANALYSIS

The research analysis plan will include a repeated measures multi-factorial analysis of variance to analyze continuous data for the functional grip and pinch measurements, with an analysis of covariance to rule out any confounding variables between groups. For Objective 1 of the randomized controlled trial of the study continuous data will be analyzed with change score analysis from baseline to end of study. To compare groups post-hoc Bonferroni will be used. Non-parametric statistics using the Friedman's Test will be used with the Numeric Pain Rating Scale, Visual Analogue Scale, and Boston Carpal Tunnel Questionnaire.

For Objective 2, qualitative data will be analyzed for thematic coding. Transcripts will be individually read and coded for emerging themes by the research team and then analyzed as a group to increase rigor. For Objective 3 to explore concepts of adherence to interventions with carpal tunnel syndrome, triangulation will be used with data obtained through interviews and with journals using a deductive approach to explore Kinesio Tape on performance. Data will be analyzed until redundancy is achieved.

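### For grip and pinch, the post-hoc Bonferroni step is valid but conservative with three groups; a Shaffer step-down never rejects less and usually finds more, provided two hands from one participant are allowed for

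*Combined protocol and SAP*

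**What the plan says.** Section 11 (Data Analysis) plans a repeated measures analysis of variance for grip and pinch, with an analysis of covariance for confounders. For Objective 1, "continuous data will be analyzed with change score analysis from baseline to end of study". The next sentence is "To compare groups post-hoc Bonferroni will be used". The pain scales and the Boston questionnaire are then handled separately: "Non-parametric statistics using the Friedman's Test will be used with the Numeric Pain Rating Scale", and the same test is named for the Visual Analogue Scale and the Boston questionnaire.

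Section 8c, item 8, fixes the number of arms: "Randomly assign participants using a random number generator, to one of three groups" (dorsal tape, sham tape, usual protocol). Section 6 gives the size: "Based on a power analysis, 64 participants are needed", then 20% attrition, "increasing the total number of participants to 78, with 26 in each of three groups". Sections 6 and 8c also say that, in a participant with symptoms on both sides, each limb is its own unit and both limbs receive the same allocation.

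The plan does not give alpha, the number of comparisons, an order among them, a reason for Bonferroni or a request for simultaneous intervals.

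**The concern.** Under the usual reading, Bonferroni tests each of three pairs at 0.05/3 = 0.0167. That protects against several pairwise nulls being true together. With three groups, however, any two pairwise nulls imply the third. Either all three are true, or at most one is. Once the first possibility has been rejected at 5%, only one false rejection can remain, and each remaining pair can be tested at the full 5%. Bonferroni does not use this fact.

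At stake is the chance of saying which arms differ in strength, in a trial with about 21 evaluable participants per arm. The stated primary purpose compares tape with splint and exercises, so that pair is the natural one to examine.

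**Working it through.** **The plan's own figure.** 64 × 1.2 = 76.8, so 77, rounded to 78 for three equal arms of 26. Dividing instead, 64/0.8 = 80. The 64 cannot be reproduced because no inputs are given. It matches a one-way three-group ANOVA with f = 0.40, 80% power and 5% alpha, but other settings give 64 too. Evaluable per arm: 64/3 = 21.3, taken as 21.

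**Assumptions.** Two-sided 5% family-wise level; all three pairs tested; independent participants; equal variances; pooled-variance t tests on 3 × (21 − 1) = 60 degrees of freedom. Differences are in units of the SD of the change score.

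**Procedures compared.**
- Bonferroni: reject a pair if p < 0.05/3.
- Shaffer: if the smallest p is below 0.05/3, reject that pair and test the other two at 0.05 each.
- Closed F: if the overall F test has p < 0.05, test each pair at 0.05.

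**Why Shaffer keeps 5%.** If all three nulls are true, a false rejection needs the smallest p to be below 0.05/3, which has probability at most 3 × 0.05/3 = 0.05. If exactly one null is true, that pair is never tested above 0.05. No other case exists with three groups. Every Bonferroni rejection is also a Shaffer rejection.

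**Bonferroni power by formula, 0.8 SD.** Noncentrality = 0.8 × √(21/2) = 2.59. The critical t at 0.0167 on 60 degrees of freedom is about 2.46. Power ≈ Φ(2.59 − 2.46) = Φ(0.13), about 55%. This does not depend on the third arm.

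**Simulated family-wise error (400,000 trials, 21 per arm).**

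| True state | Bonferroni | Shaffer | Closed F |
|---|---|---|---|
| All arms equal | 4.4% | 4.4% | 5.0% |
| One arm far apart, two equal | 1.7% | 5.0% | 5.0% |

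**Simulated power for tape versus usual protocol.**

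| Difference | Position of sham | Bonferroni | Shaffer | Closed F |
|---|---|---|---|---|
| 0.5 SD | equal to usual | 21% | 25% | 27% |
| 0.8 SD | equal to usual | 55% | 63% | 66% |
| 0.8 SD | midway between usual and tape | 55% | 57% | 60% |
| 0.8 SD | 0.4 SD below usual | 55% | 71% | 72% |
| 1.0 SD | equal to usual | 78% | 85% | 86% |

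Separate runs differ by up to about one point; the midway row also came out as 56%, 58% and 60%.

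**What does not improve much.** At 0.8 SD with sham equal to usual, the chance of finding at least one difference is 71.6% with Bonferroni, the same with Shaffer, and 74.8% with closed F. The gain lies in identifying which pairs differ: both true differences are found in 39% of trials with Bonferroni, 55% with Shaffer and 58% with closed F.

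**Hands treated as independent.** Assume half the participants are bilateral, the between-hand correlation is 0.5, and every hand is analysed as its own unit. With all arms equal, family-wise error is about 9% for Bonferroni, the same for Shaffer (identical first step), and about 10% for closed F. With one arm far apart it is about 3.7% for Bonferroni and 8.9% for the other two.

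**The case against.** The strongest reply is that Bonferroni is valid, familiar and simple, and that choosing it is not a mistake. That stands: this is an efficiency point only.

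Several stronger readings are tempting, and the documents do not support them.
- *That the step weakens the whole primary comparison.* Section 8 defines the purpose by pain, strength and function. Section 11 applies change scores to continuous data, which it identifies as grip and pinch, and sends pain and the Boston questionnaire to Friedman's test. The gain reaches strength only.
- *That the plan fixes a 0.0167 threshold.* It does not; alpha and the count of pairs are inferred.
- *That the detectable difference at 80% power falls from 1.03 SD to 0.88 SD.* The 0.88 belongs to a 5% test with no gate. With the overall F gate and sham equal to usual, about 0.92 to 0.93 SD is needed.
- *That the gain is always large.* Section 9 itself allows that the shoulder site may help. If sham falls midway, the gain is only 2 points with Shaffer and 4 to 5 with closed F.

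It can also be said that, if tape versus usual protocol is what matters, testing it first at 5% gives 72 to 73% at 0.8 SD wherever sham lies. That is correct, but it needs an order of comparisons that the plan does not state. Shaffer needs none.

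The most serious reply concerns the unit of analysis. With hands counted separately, Bonferroni's slack happens to keep error below 5% when one arm differs, and a sharper procedure removes that slack. This stands, and it is why the change must come with an allowance for paired hands. It does not rescue Bonferroni, which also fails when all arms are equal.

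**Conclusion.** The point holds as a cheap improvement limited to grip and pinch change scores. Bonferroni is valid given independent units, but conservative. At 0.8 SD, Shaffer adds about 8 points of power for tape versus usual protocol if sham equals usual, about 2 if sham is midway and about 16 if sham is 0.4 SD lower. Closed F adds a little more, but unlike Shaffer it can occasionally miss a pair that ungated Bonferroni finds (at most about 0.5% of simulated trials).

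These sizes rest on the assumed 5% level, three pairs, 21 independent participants per arm and equal variances, and on a one-way comparison of change scores rather than the full repeated-measures or covariance model. The logic for three groups does not depend on the effect size. Neither procedure adjusts for testing both grip and pinch.

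**What to change.** Replace the Bonferroni sentence in section 11 with:

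> For grip and pinch change from baseline to Visit 5, the three pairwise group comparisons use the Shaffer step-down: if the smallest p-value is below 0.05/3, the remaining pairs are each tested at 0.05; the analysis allows for two hands from the same participant (for example a per-participant mean or a participant random effect).

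State beside it that the family-wise level is two-sided 5%, if that is what is intended. Because both hands of a bilateral participant receive the same allocation, a per-participant mean loses no group comparison.

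The change needs no extra participants, visits or data, and should be made before the analysis. Its cost is in reporting: simultaneous confidence intervals no longer match the tests exactly. Ordinary 95% intervals should be reported and labelled as unadjusted, with a note that such an interval can exclude zero when the step-down does not reject.

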The primary purpose of this randomized controlled trial graduate student research study is to explore the effect of dorsal application of Kinesio Tape on occupational performance as measured by pain, strength, and function of individuals with carpal tunnel syndrome forearm wrist hand pain as compared to the usual and accepted most common non-surgical intervention of lumbrical stretching exercises and general cockup splint. The secondary purpose is to explore changes in occupational performance through semi-structured interviews in order to understand if Kinesio Tape contributed to results and if so, how. In order to help us understand how the participants perceived the interventions, the third purpose is to explore concepts of adherence to interventions with carpal tunnel syndrome.

b. Objectives

1. Determine if the dorsal application of Kinesio Tape applied to the wrist extensors for individuals with carpal tunnel syndrome and forearm wrist hand pain makes a difference in occupational performance as measured by pain, strength, and function.
2. Explore the perspectives of participants to understand if Kinesio Tape contributed to changes in occupational performance, and if so, how.

3. Explore concepts of adherence to interventions with carpal tunnel syndrome.

c. Procedures involved (Research Interventions)

The following procedures will be used for this multi-method study design that consists of a randomized control trial and descriptive qualitative study, upon IRB approval:

1. Recruit via snowballing, word-of-mouth, flyers, emails, and social media (See Appendix A)
2. Respond to study interest via Phone Script to answer questions regarding the study (See Appendix B) and set up a meeting time to review consent and initiate study procedures.
3. Review Informed Consent, HIPPA documents, and Patient's Bill of Rights and obtain consent from those interested in participating in study.
4. Screen participants for inclusion criteria by administering the Phalen's Test or Tinel's Test (Appendix C).
5. Administer Demographic questionnaire (Appendix D).
6. Administer baseline Week One Visit One Boston Carpal Tunnel Questionnaire, Numeric Pain Rating Scale, Visual Analogue Scale (Appendices E – F - G). If participant has symptoms in both extremities, the researcher will use each extremity as a separate unit and apply corresponding intervention to both extremities.
7. Collect Week One Visit One Baseline Grip and Pinch measurements (Appendix H).

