9. DATA COLLECTION

Data collection procedures on the affected extremity include psychometric assessments of pain, using the Numeric Pain Rating Scale and Visual Analogue Scale. Occupational performance will be measured using the Boston Carpal Tunnel Questionnaire completed by the participants and grip and pinch from each participant will be recorded by the student research assistants.

At the final visit, the student researcher and/or student research assistants will conduct a 30-minute 6-item semi-structured interview exploring the intervention group participant's perception of wearing Kinesio tape and its impact on the participant's occupational performance.

Study intervention will be held at the beginning of the week and the end of the week during various times of day to account for sign and symptoms related to occupation and activities of daily living. The researchers know which intervention is being studied; however, the participants will not know which intervention is being studied to increase accuracy of findings. The benefit of blinding participants in this graduate student randomized controlled trial to the objective of the study is to determine if there is indeed a benefit of the intervention of dorsal application of Kinesio Tape versus the usual protocol or current care of splint and lumbrical exercises for carpal tunnel syndrome forearm wrist hand pain. There Kinesio Tape application on the shoulder is to determine if there is an intervention effect is evidence to suggest even that application site could be beneficial. All participants will be emailed the results of the study.

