Participants will complete a demographic questionnaire at baseline, which will include age, gender, ethnicity, current occupation and duration in that position. The demographic information will be used during data analysis to determine the influence of these variables on study outcomes. Participants will complete the Numeric Pain Rating Scale and Visual Analogue Scale to allow a subjective measure of participants experiencing mild to moderate carpal tunnel syndrome forearm wrist hand pain, which will be completed at baseline, weeks one, two, and three. These assessment tools are self-report measures using ordinal data with superior sensitivity, test retest reliability ($r = 0.96$ and 0.95) as well as construct validity ($r = 0.86$) (Hawker, Mian, Kendzerska, & French, 2011; Hjermstad et al., 2011). The student researcher and/or student research assistants at baseline will record functional grip at weeks one, two, and three using a calibrated Jamar Dynamometer and standardized protocol and position. The dynamometer is the only available tool to objectively measure functional grip

strength necessary to complete occupations of work, activities of daily living, household, and work tasks and demonstrates high test-retest reliability ($r > 0.80$), inter-rater reliability ($r = 0.98$) and concurrent validity (Roberts et al., 2011). Pinch strength will be collected by the student researcher or student research assistants at baseline, weeks one, two, and three using a calibrated pinch meter with standardized protocol and position as it is a commonly available tool to objectively measure functional pinch strength necessary for fine motor control, hand use for occupations and tasks of daily living skills. The pinch meter demonstrates high inter-rater reliability ($r = 0.97$) and test re-test reliability ($r = 0.80$) (Mathiowetz et al., 1985).

Participants will also complete an 11-question standardized Boston Carpal Tunnel Questionnaire a commonly accepted subjective measure of function and severity as it relates to carpal tunnel syndrome and efficacy related to functional activities using an ordinal scale. The Symptom Severity Scale demonstrates high test-retest reliability ($r = 0.91$), with internal consistency of 0.80 – 0.90, and the Functional Status Scale also demonstrates high test-retest reliability ($r = 0.93$) with internal consistency of 0.88 – 0.93 (Carvalho Leite, Jerosch-Herold, & Song, 2006).

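### Pain and function have no named between-group test: the NPRS, VAS and Boston questionnaire are assigned only to Friedman's test, which compares visits within people and not the three randomised arms

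*Combined protocol and SAP*

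**What the plan says.** Section 8a gives the primary purpose as the effect of dorsal tape on pain, strength and function "as compared to the usual and accepted most common non-surgical intervention of lumbrical stretching exercises and general cockup splint". Section 9 repeats the contrast: "dorsal application of Kinesio Tape versus the usual protocol or current care of splint and lumbrical exercises". Participants are randomised to three arms: dorsal tape, sham tape and usual protocol.

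Section 11 then assigns methods by type of outcome:

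- Grip and pinch: "repeated measures multi-factorial analysis of variance to analyze continuous data for the functional grip and pinch measurements", with an analysis of covariance.
- Objective 1: "continuous data will be analyzed with change score analysis from baseline to end of study".
- Group comparison: "To compare groups post-hoc Bonferroni will be used".
- Pain and function: "Non-parametric statistics using the Friedman's Test will be used with the Numeric Pain Rating Scale, Visual Analogue Scale, and Boston Carpal Tunnel Questionnaire".

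Section 9 describes the two pain scales thus: "These assessment tools are self-report measures using ordinal data". It also describes the Boston questionnaire as scored on an ordinal scale.

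**The concern.** The primary purpose is a contrast between arms. Friedman's test is for related measurements. The three arms are different people, so the only related measurements are one person's visits, and the test can only ask whether scores change over time.

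Scores may improve in every arm through natural course, regression to the mean or placebo response. A significant Friedman result is then expected even if tape adds nothing. Conversely, arms that move in opposite directions can cancel in the pooled test. If the test is run separately by arm, the temptation is to read significance in the tape arm and none in the usual-protocol arm as a treatment effect, which it is not. The plan does not say whether the test is pooled or run by arm.

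**Working it through.** **1. Which method reaches which outcome**

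| Outcome | Data type in section 9 or 11 | Method named in section 11 | Contains a group term? |
|---|---|---|---|
| Grip, pinch (strength) | Continuous | Repeated-measures ANOVA, ANCOVA, change score | Yes |
| NPRS, VAS (pain) | Ordinal | Friedman | No |
| Boston questionnaire (function) | Ordinal | Friedman | No |

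No Kruskal-Wallis, Mann-Whitney, rank ANCOVA or ordinal model is named anywhere in the document.

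**2. What Friedman's statistic contains**

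With n people, k visits and R_j the sum of within-person ranks at visit j:

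Q = 12 / [n k (k+1)] × Σ R_j² − 3 n (k+1)

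No arm index appears, so shuffling the arm labels leaves the pooled Q unchanged. Computed by arm, each Q uses that arm's people only.

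Two extreme cases use k = 5 visits and 21 completers per arm (26 × 0.8 = 20.8), so n = 63:

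- *Everyone in all three arms changes steadily in the same direction.* R_j = 63j and Σ R_j² = 63² × 55 = 218,295. Q = 12 × 218,295 / 1,890 − 1,134 = 1,386 − 1,134 = 252. This is the maximum, n(k−1) = 63 × 4, although the arms rank identically.
- *One arm falls steadily, one rises steadily, one is flat (tied, rank 3 throughout).* R_j = 21j + 21(6−j) + 63 = 189 at every visit. Q = 12 × 5 × 189² / 1,890 − 1,134 = 1,134 − 1,134 = 0. The arms differ completely and the test sees nothing.

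**3. Illustration by simulation**

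The documents give no SD, correlation or expected change, so all of these are assumed: 21 per arm, five visits, a rounded 0–10 score, SD 2, linear improvement equal in all arms, no group difference, 5% level, 4,000 trials per setting.

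| Between-visit correlation | Improvement (SD) | Pooled Friedman significant | Arms disagree on significance | Tape significant, usual not |
|---|---|---|---|---|
| 0.4 | 0.3 | 0.378 | 0.344 | 0.112 |
| 0.4 | 0.5 | 0.850 | 0.662 | 0.221 |
| 0.4 | 0.8 | 0.999 | 0.562 | 0.186 |
| 0.6 | 0.3 | 0.554 | 0.466 | 0.157 |
| 0.6 | 0.5 | 0.959 | 0.748 | 0.247 |
| 0.6 | 0.8 | 1.000 | 0.231 | 0.074 |
| 0.8 | 0.3 | 0.867 | 0.690 | 0.232 |
| 0.8 | 0.5 | 1.000 | 0.457 | 0.156 |
| 0.8 | 0.8 | 1.000 | 0.004 | 0.001 |

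Over the same settings, Kruskal-Wallis on change rejects in 0.044–0.055 and rank ANCOVA in 0.045–0.057. At correlation 0.6 with no improvement at all, pooled Friedman rejects in 0.046. With arms changing by +0.6, 0 and −0.6 SD (a real difference with no average change), pooled Friedman rejects in 0.030 and Kruskal-Wallis on change in 0.959.

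**4. A condition on any replacement test**

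For people with symptoms on both sides, section 6 says "the researcher will use each extremity as a separate unit and apply corresponding intervention to both extremities". With 30–60% bilateral, between-hand correlation 0.5–0.8 (both assumed), between-visit correlation 0.6 and no group difference (3,000 trials per setting), testing hands as independent rejects in 0.084–0.153 (Kruskal-Wallis) or 0.079–0.156 (rank ANCOVA). On person means the rates are 0.044–0.049 and 0.048–0.053.

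**The case against.** The strongest reply is that the plan does intend to compare groups. The Bonferroni sentence is not expressly limited to grip and pinch, and it comes just before the Friedman sentence. Section 11 lists what the analysis will include, which need not be exhaustive, and section 9 foresees examining demographic influences on outcomes. The intent is granted. But Bonferroni adjusts p-values from a test and is not itself a test. None is named for these scales, and post-hoc comparisons after Friedman compare visits.

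The VAS could be treated as continuous and so brought under the change-score analysis. Section 9 calls it ordinal and section 11 lists it under Friedman; even if it were moved, the NPRS and Boston questionnaire would stay uncovered.

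The simulation can fairly be discounted. Its wide ranges reflect the assumed improvement, and a pooled rejection is a correct detection of change over time. It becomes an error only if read as a treatment effect, which the plan does not say it will do. That stands, so the figures serve only as illustration.

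Two hands per person and missing final scores are separate matters that also affect grip and pinch. They condition the remedy and add no weight here. Finally, the primary purpose is worded as exploratory and strength has a between-group model; but the same sentence specifies a comparison with usual care.

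**Conclusion.** The concern holds. As written, the plan names no between-group test for pain or function, two of the three Objective 1 domains, although randomisation makes one available. Neither a pooled nor a by-arm Friedman test can support a claim that tape is better or worse than splint and exercises. This follows from the construction of the test and from the allocation of methods in section 11, and rests on no assumed figure. The simulated rates depend wholly on the assumptions listed. Grip and pinch are not affected. The point should be settled before analysis, because otherwise the comparative test would be chosen with the data in view.

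**What to change.** Revise section 11 so that the Objective 1 analysis of each of the NPRS, VAS and Boston questionnaire scores compares the three arms at Visit 5, adjusted for that scale's baseline score, by rank ANCOVA or a proportional-odds model, with Bonferroni-adjusted pairwise comparisons. An ordinal mixed model with arm, visit and their interaction is a legitimate alternative that also uses Visits 2–4. The minimum is Kruskal-Wallis on change from baseline to Visit 5 with Bonferroni-adjusted pairwise rank tests, though ranking differences treats the scale as closer to interval than section 9 does.

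In the same paragraph:

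- Analyse at person level or with a model clustered by person. Clustering, or the mean of both hands, changes the analysis only, although a mean again assumes interval-like scores. Fixing one hand before randomisation would also require edits to sections 6 and 8.
- State how a missing Visit 5 score is handled, given the 20% attrition expected in section 6.
- State whether multiplicity is controlled across the scales as well as across pairs of arms.
- Keep Friedman's test, if wanted, as within-arm description that supports no claim of benefit.

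The cost is a rewritten paragraph and a little extra analysis, with no new data or visits. Power cannot be confirmed, because section 6 does not say which outcome or test the 64 participants were based on. In one assumed setting (improvement of 0.8, 0.2 and 0.4 SD in tape, sham and usual protocol, correlation 0.6, 21 per arm), Kruskal-Wallis on change rejected in 42% of trials, so adequate power should not be presumed.
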